4 STUDY DESIGN

4.1 OVERALL DESIGN

This RCT will enroll 174 patients with pain due to musculoskeletal injuries to test the efficacy of a multi- model digital pain reduction kit on short term pain management as an adjunct to traditional medical therapy. We will attempt to enroll a minimum of 90 patients reporting lower back pain specifically, as patients without lower back pain are less likely to use the TENS unit. Prior to adding the TENS unit to the control arm, we recruited 24 control patients. However, we will not discard their data since we intend on performing a supplementary sensitivity analysis. In addition to these 24 controls, we will randomize 75 patients to receive the study intervention (multi-modal digital pain-reduction kit with optional remote coaching support), and the other 75 patients will receive an active control. We will allocate patients using a random number generator to ensure that there is an equal distribution of participants in the control vs. experimental group. The primary outcome will be changes in self-reported physical function measured by the Patient Reported Outcome Measurement Information System (PROMIS®) Physical Function Scale. Secondary outcomes will include PROMIS® Pain Interference Scale, PROMIS® Global Health Scale, work productivity and activity impairment questionnaire (WPAI) (for patients with lower back pain specifically), patient satisfaction measured by the Pain Treatment Satisfaction Scale and SF Patient-Satisfaction Questionnaire), and use of opioids (measure in morphine milligram equivalents).

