Use and satisfaction with the TENS device will be monitored via daily questionnaires administered by either LifeData or Redcap (as described above).

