9.4.4 ACCOMODATING ADDITION OF TENS UNIT TO THE CONTROL ARM

An ITT analysis "Includes all randomized patients in the groups to which they were randomly assigned, regardless of their adherence with the entry criteria, regardless of the treatment they actually received, and regardless of subsequent withdrawal from treatment or deviation from the protocol."^{ref} Accordingly, we will follow the original analysis plan described above with regard to analyzing results by study-arm. In addition to the ITT analysis, however, we will conduct a sensitivity analysis by repeating the statistical procedures in a per-protocol fashion wherein the members of the control arm who did not receive a TENS unit will be dropped from the sample. Directions, magnitudes, and significance of treatment effects will be presented for both analyses.

Furthermore, because the TENS unit will appear in both study arms - and unevenly in the control arm – we recognize that an ITT analysis strictly *by* study-arm risks misidentifying the effect of treatment, while a per-protocol analysis risks introduction of bias. Therefore, we will conduct an additional linear mixed model regression analysis using a term for the TENS that captures the effect of the TENS separately from the effects of study-arm assignment. The model used to fit these data is as follows:

 $\hat{y}_{it} = \beta_0 + \beta_1 time_{it} + \beta_2 study_arm_{it} + \beta_3 TENS_{it} + e_{it}$

where time represents change in time from baseline, study_arm indicates status as a control or experimental participant (0= control and 1=experimental), *i* is the individual participant, and TENS indicates TENS unit usage (0= no TENS unit and 1=TENS unit). We can therefore write a regression equation describing each type of patient differentiated by the addition of the TENS unit to control conditions:

Treatment: $\hat{y}_{it} = \beta_0 + \beta_1 time_{it} + \beta_2 study_arm_{it} + \beta_3 TENS_{it} + e_{it}$

Control w/o TENS: $\hat{y}_{it} = \beta_0 + \beta_1 time_{it} + e_{it}$

Control w/ TENS:

 $\hat{y}_{it} = \beta_0 + \beta_1 time_{it} + \beta_3 TENS_{it} + e_{it}$

In this manner we isolate the term of interest (study_arm). Given we are only adding one term but 20 subjects, we are comfortable relying on the original power calculation.

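### The TENS-term model in 9.4.4 returns the per-protocol level contrast, so it can neither remove nor independently check bias in that analysis

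*Combined protocol and SAP*

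**What the plan says.** Section 9.4.4 plans three analyses to deal with the addition of TENS to the control arm.

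1. A by-arm ITT analysis.
2. A per-protocol repeat of the statistical procedures in which "the members of the control arm who did not receive a TENS unit will be dropped from the sample". Section 9.4.2 makes those procedures two: a random-intercept linear mixed model on the repeated scores, and a difference-in-differences on change from baseline to the end of the intervention.
3. A further model. The section says the by-arm ITT may misidentify the treatment effect while "a per-protocol analysis risks introduction of bias". As a consequence, "we will conduct an additional linear mixed model regression analysis using a term for the TENS that captures the effect of the TENS separately"; the aim is to keep it apart from the arm effect.

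The printed model has time, study_arm and TENS. It has no arm-by-time, covariate or enrolment-period term. TENS is 0 for no unit and 1 for a unit. The section concludes "In this manner we isolate the term of interest (study_arm", and then "Given we are only adding one term but 20 subjects, we are comfortable relying on the original power calculation".

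Sections 1.1, 4.1 and 6.2 give 75 intervention patients, 75 controls with TENS and 24 controls without. Section 4.1 says the 24 were recruited before the change. Sections 4.1 and 6.2 assign them to a supplementary analysis, whereas 9.3 and 9.4.4 leave them in the ITT set.

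**The concern.** The plan introduces the third analysis as the way out of weaknesses it sees in the first two. That works only if its arm coefficient is something other than the per-protocol comparison. If it is the same comparison, the level models give two distinct arm contrasts, not three. Agreement between the second and third analyses would then follow from the algebra, whether or not the contrast is biased.

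This matters because Section 3 states the primary comparison against an active control, and the current control has TENS. The per-protocol rule drops the early controls but keeps every intervention patient. Any intervention patient randomised before the change is therefore compared only with later controls.

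**Working it through.** **The plan's own figure.** Section 9.4.4 relies on the calculation in 9.2 (0.6 SD, 80% power, 0.05, 25% withdrawal). Two-sided, n per arm = 2(1.96 + 0.842)²/0.6² = 43.6, so 44. Then 44/0.75 = 58.7, so 59 per arm and 118 in total (60 and 120 by t test). Section 9.2 prints about 120 per arm and 245 in total, which does not reproduce; 120 fits only as a total. This is a separate matter, and nothing below depends on it.

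**The arm coefficient.** From the three group equations in 9.4.4:

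- Treatment: b0 + b1·time + b2 + b3
- Control with TENS: b0 + b1·time + b3
- Control without TENS: b0 + b1·time

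Treatment minus control with TENS is b2 (study_arm). Control with TENS minus control without is b3. Section 6.1.1 gives every intervention patient a TENS device, so no cell has arm = 1 and TENS = 0. The 24 early controls identify b3. They reach b2 only through the shared slope, covariate and variance estimates.

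**Numerical check.** The TENS model on 174 patients was compared with the time-plus-arm model on the 150 per-protocol patients, using random intercepts and the ten scheduled PROMIS visits. SD 10, ICC 0.7, 15% missed surveys and covariates explaining 20% of between-patient variance are assumptions. The 25% withdrawal is from 9.2.

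- Complete data, no covariates: equal to rounding error.
- 25% withdrawal plus 15% missed surveys: mean difference 0.002 to 0.003 points, largest 0.027 across repeated runs. A separate REML run with other variances gave at most 0.016 over 240 simulated trials, with correlation above 0.9999.
- 13 covariates (the number listed in 9.1) in both fits: mean difference 0.12 to 0.14, largest 0.60, against an SE of about 1.4 to 1.5.

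**Precision from the early controls.** The SE ratio for study_arm is 0.999996 without covariates. With 13 it is 0.9939: 1/0.9939² − 1 = 1.2%, or about 1.9 patients in 150.

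**Where the identity stops.** The printed model has no arm-by-time term, so b2 is a difference in levels averaged over visits. The difference-in-differences uses final minus baseline. Under a random-intercept model with complete data, the visit average has the same covariance with the first and the last score, so the two estimates are uncorrelated. They compare the same groups but estimate different things.

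**Period bias as a function of e.** The sizes are illustrative assumptions, and the bias scales in proportion to them. Case A: early patients score 3 points higher throughout. Case B: early patients gain 2 extra points by day 60, linearly. The ramp (day − 1)/59 averages 303/590 = 0.514 over the ten visits.

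| e | 0 | 12 | 24 | 36 |
|---|---|---|---|---|
| A, study_arm and per-protocol level model: 3e/75 | 0 | 0.48 | 0.96 | 1.44 |
| A, per-protocol change | 0 | 0 | 0 | 0 |
| B, study_arm and per-protocol level model: 2 × 0.514 × e/75 | 0 | 0.16 | 0.33 | 0.49 |
| B, per-protocol change: 2e/75 | 0 | 0.32 | 0.64 | 0.96 |
| Both arms after the change only | 0 | 0 | 0 | 0 |
| Power of that contrast at 0.6 SD | 89% | 86% | 82% | 75% |

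In case B with no true TENS effect, the TENS coefficient is −2 × 0.514 = −1.03, because it compares early with later controls. Power uses SE = √(1/(0.75(75 − e)) + 1/56.25) in SD units; at e = 24 this is 0.2096, and 0.6/0.2096 − 1.96 = 0.90, or 82%.

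**Effect of a before/after term p.** The cells become early intervention b0 + b2 + b3 + p, early control b0 + p, late intervention b0 + b2 + b3 and late control b0 + b3. Four cells have four parameters, so b2 is late intervention minus late control: the after-change contrast. At e = 0 the term equals 1 − TENS and cannot be estimated beside it.

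**The case against.** The strongest reply is that the per-protocol analysis repeats both procedures in 9.4.2, and the identity holds for only one. That stands: the difference-in-differences result is not duplicated, and the table shows its period bias differs. The point is limited to the random-intercept level model.

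Second, 9.4.4 never says the TENS model confirms the per-protocol result. That also stands; its stated aims are to separate TENS from arm and to avoid the problems of the other two analyses. The second aim is what fails. Misreading agreement as support is a risk to forestall, not something the plan does.

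Third, TENS might mean actual use: the text says "TENS indicates TENS unit usage", 8.1 states "Use and satisfaction with the TENS device will be monitored via daily questionnaires", and 4.1 expects that "patients without lower back pain are less likely to use the TENS unit". Entering actual use would break the identity, but would condition study_arm on behaviour after randomisation. The 0/1 definition and the group equations point to provision. A reader might take the t subscript as evidence of time-varying use, but study_arm, fixed per patient, carries the same subscript.

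Fourth, the power sentence reaches a tolerable conclusion, since adding the term costs study_arm no precision. That stands. Its reason does not, because the added subjects hardly inform study_arm.

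Fifth, encounter month could absorb drift. Section 9.1 lists it only as a potential covariate and the printed model omits it. Added to both fits, it would leave them comparing the same groups.

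**Conclusion.** The point holds for the level mixed model, given TENS coded as unit provided. There study_arm is the per-protocol contrast, exactly with complete data and no covariates and very nearly otherwise. The model cannot remove or independently check bias in that analysis. What it adds is a TENS coefficient that mixes TENS with calendar period.

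A reader might go further and infer that the kit versus TENS-control comparison is biased. The documents do not support that. They do not state e, and the wording of 4.1 and 6.2 does not settle it. If e = 0 the per-protocol contrast is concurrent and has no period bias. If e > 0 the two level models share whatever period bias exists, and its size cannot be computed from the documents; the table only illustrates it. The redundancy holds at every e.

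The by-arm ITT remains in the plan, so no result is invalidated. A stated safeguard does not do what is claimed for it, and this should be corrected before analysis.

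**What to change.** 1. State e and the date on which TENS was added to the control arm.
2. Keep the all-randomised by-arm ITT. If e > 0, run the kit versus TENS-control sensitivity analysis on patients of both arms randomised after the change, or add a before/after-change term to the TENS model, which gives the same arm contrast. The term also frees the TENS coefficient of any period effect common to both arms.
3. In 9.4.4, describe study_arm as kit versus TENS control, remove the claim that the TENS model remedies per-protocol bias, and do not cite its agreement with the per-protocol level model as support.
4. Define TENS as unit provided, fixed per participant. Reword the power sentence so that it does not lean on the added subjects, and reconcile its 20 with the 24 in 1.1, 4.1 and 6.2.
5. Reconcile 4.1, 6.2, 9.3 and 9.4.4 on whether the 24 controls belong to the main ITT or only to the supplementary analysis.

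The cost is SAP wording plus randomisation dates that should already be held. The restricted contrast loses e intervention patients. Its SE rises by about 5%, 11% and 21% at e = 12, 24 and 36, and at e = 36 power falls below the planned 80%. That loss falls on a sensitivity analysis; the ITT is untouched.

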3 OBJECTIVES AND ENDPOINTS

OBJECTIVES	ENDPOINTS	JUSTIFICATION FOR ENDPOINTS
Primary		
The primary objective of this study is to develop and validate a multi- modal digital pain reduction kit for improving physical function over time.	The primary endpoint in this study is a clinically significant change in self- reported physical function over time among individuals in the intervention arm compared to those in the active control. The outcome measure used to quantify this endpoint is the PROMIS® PF short-form, a validated self-report of physical function. The	The PROMIS® PF short- form scale is a widely validated instrument with excellent content validity, construct validity, and reliability in patients with spinal disorders and other conditions marked by

OBJECTIVES	ENDPOINTS	JUSTIFICATION FOR ENDPOINTS
	outcome measure is administered on a weekly basis via a smartphone survey to capture longitudinal change and variation among participants.	diminished mobility. The outcome measure allows us to place patients on a continuum of physical function with respect to various physical actions.
Secondary		
The secondary objective of this study is to investigate the efficacy of a multi-modal digital pain reduction kit in reducing pain interference over time, work productivity, opioid use, and satisfaction with care.	The secondary endpoints of are clinically significant changes in pain interference, work productivity, use of opioids, and satisfaction with healthcare among those in the intervention arm compared to participants in the active control. Outcome measures include pain interference (PROMIS® Pain Interference, measured weekly via smartphone surveys), work absenteeism and presenteeism (WPAI:LB, measured at baseline and exit surveys), number of 90 Morphine Milligram Equivalent opioid prescriptions (obtained via cumulative EHR records), and satisfaction with healthcare (CG- CAHPS, measured once at the conclusion of the study).	
Tertiary/Exploratory		
N/A	N/A	N/A

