9 STATISTICAL CONSIDERATIONS

9.1 STATISTICAL HYPOTHESES

• Primary Efficacy Endpoint(s):

Primary Outcome: Physical function over time as measured by PROMIS PF score (T- Scored, Continuous)

Question: Which intervention is more effective in improving physical function?

Independent variable of interest: Comparator received, intervention vs. control (Dichotomous)

Potential Covariates: Age, gender, race, ethnicity, mental health comorbidities, chronic pain diagnosis, use of other pain medications (neuropathic pain medications, NSAIDS, antidepressants), benzodiazepine use, number of office visits during study period, baseline PROMIS[®] scores, encounter month, physician years of practice, physician gender.

• Secondary Efficacy Endpoint(s):

Secondary Outcome: Pain over time as measured by PROMIS Pain Interference Score (T-Scored, Continuous)

Question: Which intervention is more effective in improving patient's pain interference?

Independent variable of interest: Comparator received, intervention vs. control (Dichotomous).

Potential Covariates: Same as Primary Aim.

Secondary Outcome: Effects of lower back pain symptom severity on work productivity and regular activities over time as measured by WPAI:LB (T-Scored, Continuous).

Question: Which intervention is more effective in improving patient's work productivity and participation in regular activities?

Independent variable of interest: Comparator received, intervention vs. control (Dichotomous).

Potential Covariates: Same as Primary Aim.

Secondary Outcome: New Opioid Prescription over 90MME (Dichotomous)

Question: Which intervention is more effective in reducing opioid prescriptions of 90 Morphine Milligram Equivalents (MME) or greater?

Independent variable of interest: Comparator received, intervention vs. control (Dichotomous).

Potential Covariates: Same as Primary Aim.

Statistical Analyses: As in the primary aim analyses, we will employ mixed effects models featuring both fixed effects and random effects to account for within subject variation.

Because this particular outcome is binary, we will use mixed logistic regressions in which the log odds of the outcomes are modeled as a linear combination of the predictors.

Secondary Outcome: Satisfaction with Pain Treatment and Healthcare Scores

Question: Which intervention is more effective in improving how satisfied patients feel with their care?

Dependent variable: Pain Treatment and Patient Satisfaction Scores

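### The supplementary TENS model in 9.4.4 leaves y undefined and omits baseline physical function; defining y as post-baseline scores and adding Day 1 PF is a cheap gain in clarity and precision

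*Combined protocol and SAP*

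**What the plan says.** To handle the controls recruited before TENS was added to the control arm, section 9.4.4 states that "we will conduct an additional linear mixed model regression analysis using a term for the TENS". The printed equation has an intercept, time, study_arm, TENS and an error term. The explanation starts "where time represents change in time from baseline" and goes on to define study_arm, the participant index and TENS. It does not define y. It concludes: "In this manner we isolate the term of interest (study_arm)".

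Elsewhere the outcome is described in two ways. Section 3 says "The primary endpoint in this study is a clinically significant change" and section 4.1 says "The primary outcome will be changes in self-reported physical function", so both speak of change. Section 9.1 names the score itself: "Physical function over time as measured by PROMIS PF score". Section 9.1 also lists baseline PROMIS scores, but only among potential covariates. Section 9.4.2 plans random-intercept mixed models and a difference-in-differences from baseline to the end of the intervention. Section 9.4.4 also plans "repeating the statistical procedures in a per-protocol fashion", leaving out the controls without TENS. The schedule in section 1.3 has PROMIS on Day 1 and at nine later times (Days 7 to 56 weekly, and Day 60).

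**The concern.** The plan introduces this model because it sees a weakness in each of the other two analyses. It says that analysing strictly by arm may misidentify the treatment effect, and that "a per-protocol analysis risks introduction of bias". The model's arm coefficient should therefore have a stated meaning and use the data already in hand. As printed, a reader cannot tell whether it is a difference in level or in change, or which visits it averages over.

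Two things are at stake. The first is precision: Day 1 PF is probably correlated with later PF, and the equation does not use it as a covariate. The second is dilution. The PROMIS recall period is seven days (section 8.1), so a Day 1 score describes the week before any device was used. If Day 1 is a row of y, a single constant arm coefficient is averaged over one visit at which no effect can exist. In an open trial it is also better to settle these choices before the data are analysed.

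**Working it through.** **The plan's own figure.** Section 9.4.4 gives no precision for this model and relies on the calculation in 9.2 (0.6 SD, 80% power, alpha 0.05, 25% withdrawal, about 120 per arm, 245 in total). The usual formula gives 2 × (1.960 + 0.842)² / 0.6² = 43.6, so 44 per arm; 44 / 0.75 = 58.7, so 59 per arm and 118 in total. The stated 120 is close to this only as a total. Nothing below depends on it.

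**Inputs.** Ten PROMIS occasions (section 1.3); SD taken as 1; random intercept (section 9.4.2). Assumed, because the documents give no value: correlation r between visits of 0.3 / 0.5 / 0.7, equal for all pairs, and complete data. With two indicators for three groups, study_arm is the contrast of the kit arm with the TENS controls. With n per arm, let v = 2/n.

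**Three readings of y.**
- A: PF score, Day 1 included as a row.
- B: PF score, follow-up rows only.
- C: change from baseline, follow-up rows only.

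**Variance of study_arm, in units of v.**
- A: (1 + 9r)/10 = 0.370 / 0.550 / 0.730
- B: (1 + 8r)/9 = 0.378 / 0.556 / 0.733
- C: (1 + 8r)/9 + 1 − 2r = 0.778 / 0.556 / 0.333
- Follow-up rows with Day 1 PF as covariate: (1 + 8r)/9 − r² = 0.288 / 0.306 / 0.243

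Reading A averages over ten rows, one of which carries no effect, so its coefficient is 9/10 of the follow-up average. For a fair comparison its variance is divided by 0.9² = 0.81.

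**Ratio to the adjusted model.**
- A: 1.59 / 2.22 / 3.70
- B: 1.31 / 1.82 / 3.01
- C: 2.70 / 1.82 / 1.37

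With complete data these ratios do not depend on n, the effect size or how the effect builds up.

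**Sensitivity to the correlation pattern.** If correlation decays by a factor of 0.6 / 0.7 / 0.8 per week, the same contrasts give A 1.25 / 1.36 / 1.62, B 1.10 / 1.18 / 1.38 and C 3.05 / 2.41 / 1.86. The adjusted model remains the most precise, but the gain can be small.

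**Chance baseline difference.** The share passed into study_arm is 37 / 55 / 73% under A, 30 / 50 / 70% under B, and 70 / 50 / 30% with reversed sign under C. It is zero after adjustment. The SE of the chance difference is √(2/75) = 0.16 SD at 75 per arm and √(2/56) = 0.19 SD at 56 (75 less 25%). Its expectation under randomisation is zero.

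**Simulation of the three-group model (75/75/24, r = 0.6, true effect 0.60 SD from Day 7, complete data).** SE without and with Day 1 PF: B 0.131 and 0.087; C 0.109 and 0.087, both centred on 0.60. The closed forms at r = 0.6 give the same SEs.

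**Covariate added while Day 1 stays a row of y.** The SE falls from 0.131 to 0.078, but the coefficient is 0.54 both times (0.9 × 0.60). With 25% dropout the coefficients are 0.514 and 0.520 and the SEs 0.132 and 0.079, so coverage of the true 0.60 by a 95% interval falls from about 90% to about 83% (normal approximation). A diluted value is merely estimated more tightly.

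**Power, as illustration.** Section 9.2 gives no time point for 0.6 SD. If it is reached linearly at Day 60, the average share over visits is 0.514 (ten rows) or 0.571 (nine rows). At 56 per arm, power is A 76 / 59 / 48%, B 84 / 68 / 56%, C 54 / 68 / 88% and adjusted 92 / 91 / 96%. If instead 0.6 SD is the average over visits, reading A already has 96 to 99.9%.

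**The case against.** The strongest reply is that the equation is a sketch. It is called a mixed model yet prints no random effect, so a missing covariate need not mean that baseline PF will be left out, especially as 9.1 lists it. This stands in part: the intent is unclear. But 9.1 commits to nothing, and 9.4.4 presents the equation as the model to be fitted.

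A reader might infer more than the documents support:
- *That study_arm ignores baseline on any reading.* If y is change, baseline is already subtracted. That is inefficient, but it is not the same as ignoring it.
- *That the estimate is biased by baseline imbalance.* Randomisation makes the expected chance difference zero. The only shift in the expected coefficient shown here is the dilution from a Day 1 row.
- *That adding baseline PF is enough.* With Day 1 still a row of y, the dilution remains.
- *That 1.3 to 3.7 times as many patients would be needed.* That range comes from equal correlation and complete data. Decaying correlation gives ratios as low as about 1.10.
- *That the trial's conclusion is at risk.* The model is supplementary. The planned difference-in-differences, repeated without the no-TENS controls, already compares change among patients with TENS. Under equal correlation and 0.6 SD at Day 60, it has 77 to 98% power at 56 per arm. The low power figures for reading A also reflect averaging a slowly growing effect, not only the missing covariate.

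**Conclusion.** The specification gap is real and minor. The 9.4.4 model does not define y or its rows, and it has no term for a baseline score that the trial already collects. Fitted as printed, study_arm loses precision under each reading examined: its variance is about 1.3 to 3.7 times that of the adjusted model with equal correlation of 0.3 to 0.7 and complete data, and about 1.1 to 3 times with correlation decaying at 0.6 to 0.8 per week. If Day 1 is an outcome row, the coefficient is also about 10% too small with complete data, and somewhat more with dropout (0.51 for a true 0.60 in the 25% dropout simulation). The correlations, effect shapes and dropout pattern are assumptions, so the sizes are illustrative; the direction of the precision gain held in every case tried. The conclusion of the trial need not change.

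**What to change.** In 9.4.4:
1. Define y as the post-baseline PF T-score and say that Day 1 is not an outcome row.
2. Add Day 1 PF as a covariate.
3. State that study_arm is the baseline-adjusted difference between arms averaged over post-baseline visits.

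The order matters, because step 2 without step 1 leaves the dilution in place. With Day 1 PF in the model and only follow-up rows in y, study_arm is the same whether y is written as score or as change, so the wording of sections 3, 4.1 and 9.1 no longer pulls in different directions. Optionally, add arm-by-visit terms and report the end-of-intervention contrast, to match the baseline-to-end comparison in 9.4.2; this costs extra parameters.

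The cost is SAP wording and one parameter, with no new data collection. There are three small downsides to cover in the text. A patient with no post-baseline score does not contribute, although 9.3 includes all randomised participants. A rule is needed for a missing Day 1 score, which matters given the low survey compliance cited in the summary of changes. And because Day 1 follows randomisation in an open trial, the plan should say that the Day 1 score is completed before the kit is used.

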4.2 SCIENTIFIC RATIONALE FOR STUDY DESIGN

The active control group in the randomized control trial minimizes biases related to reactivity administering standard care of care in addition to a passive measurement component. Therefore, the control group may show some effect and limit the effect size of the intervention, given that TENS units have been shown to reduce pain, at least in the short term.

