6.2 MEASURES TO MINIMIZE BIAS: RANDOMIZATION AND BLINDING

Per the new protocol, participants will be randomized intervention or control until intervention and control groups each have 75 enrollees. In addition to these 150 participants, the group of 24 controls that were originally recruited without the TENS unit will remain accounted for in the supplementary analysis. There will be no blinding, as participants in the control group will be aware that they are missing components of the intervention as detailed in the consent form.

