8.1 EFFICACY ASSESSMENTS

PROMIS[®] Questionnaires

The primary outcome for this study will be self-reported physical function (PF) using the PROMIS® PF short form scale. For patients with acute pain, PF is often diminished and patients seek return to normal function. The PROMIS® PF short-form scale is a widely- validated instrument with excellent content validity, construct validity, and reliability in patients with spinal disorders and other conditions marked by diminished mobility. The instrument place patients on a continuum of function from extremely low to very high across activities that require physical actions, ranging from self-care to more complex activities that require a combination of skills. The scale is rendered using a T-statistic, where a score of 50 represents the population mean, and 10 points is a standard deviation (SD). The minimally clinically important difference (MCID) on the PROMIS® PF short form is 2 points, or 0.2 SD. [22]

Secondary outcomes will include the PROMIS[®] pain interference scale and the PROMIS[®] global health scale. The pain interference scale measures the consequences of pain on relevant aspects of one's life. This includes the extent to which pain hinders engagement with social, cognitive, emotional, physical, and recreational activities. The PROMIS[®] global health scale is an overall evaluation of one's physical and mental health. We will include this instrument to address outcomes that are not often addressed in pain interventions, including fatigue and mental health. All PROMIS[®] measures use a 7-day recall period reflecting the previous week's health status.

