9.2 SAMPLE SIZE DETERMINATION

We will power this study to detected a 0.6 standard deviation (SD) effect size in PROMIS® PF scores between arms – a value that is three-times the established minimal clinical important difference of 0.2 SD and is considered a "moderate effect" using the

rules of Cohen. Assuming an 80% power, a level of 0.05, and a 25% withdrawal rate, we calculate a minimal

sample size requirement of approximately 120 per arm, for a total of 245 patients.

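### Section 9.4.4 keeps the power calculation for a reason that fails: in the TENS-term model, the controls without TENS add essentially nothing to the study_arm estimate

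*Combined protocol and SAP*

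**What the plan says.** Section 9.4.4 keeps the by-arm ITT analysis. It adds a per-protocol sensitivity analysis that drops controls without a TENS unit, and a further linear mixed model with terms for time, study_arm and TENS. It names study_arm as the term of interest and closes: "Given we are only adding one term but 20 subjects, we are comfortable relying on the original power calculation".

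The power calculation it relies on is in section 9.2: "We will power this study to detected a 0.6 standard deviation (SD) effect size in PROMIS® PF scores between arms". The other inputs are given as "Assuming an 80% power, a level of 0.05, and a 25% withdrawal rate", and the result as a "sample size requirement of approximately 120 per arm, for a total of 245 patients".

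Section 6.2 plans 75 patients in each arm and separately counts "the group of 24 controls that were originally recruited without the TENS unit". The synopsis and section 4.1 also give 24. Section 4.2 says of the active control that "the control group may show some effect and limit the effect size of the intervention".

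**The concern.** The sentence in section 9.4.4 is the only link between the power calculation and a trial whose control arm now receives TENS. It treats the additional subjects as compensation for the additional parameter. That works only if those subjects carry information on study_arm, and in this model the controls without TENS do not.

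Two further gaps sit beside it. The number 20 matches no count of these controls elsewhere. The 0.6 SD target is also carried over without asking whether it suits a comparison of kit with TENS, although section 4.2 gives a reason to ask. A reader of a null result could take 80% power for that contrast as established when the plan has not established it.

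**Working it through.** **Inputs.** 0.6 SD, 80% power, alpha 0.05 and 25% withdrawal (section 9.2). 75 kit, 75 TENS controls and 24 controls without TENS (sections 4.1 and 6.2). SD 10 T-score points and minimal important difference 2 points (section 8.1). Ten PROMIS time points (section 1.3). Random intercepts (section 9.4.2). Assumed, because the documents do not say: two-sided testing, and a within-patient correlation of 0.5 to 0.7.

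**1. The plan's own figure.** n per arm = 2(1.960 + 0.842)² / 0.6² = 43.6, so 44. Dividing by 0.75 gives 59 enrolled per arm. The t-test version gives 45, then 60. The total is therefore 118 to 120. A one-sided test gives 35, then 47 per arm. No variant gives 120 per arm or 245 in total. The figure 120 matches the total for both arms, and 2 × 120 is 240, not 245.

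**2. What study_arm estimates.** At a given time, the three equations in section 9.4.4 imply these means, apart from the common time term:

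| Group | Mean |
|---|---|
| Control without TENS | β0 |
| Control with TENS | β0 + β3 |
| Kit | β0 + β2 + β3 |

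So β2 is kit minus control with TENS. The first row serves to estimate β3.

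**3. Standard error of study_arm, one time point, all enrolled patients, SD units.**

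- 75 versus 75 only: √(1/75 + 1/75) = 0.1633.
- With the 24 added and the TENS term fitted: 0.1633.
- With the 24 pooled into control and no TENS term (by-arm ITT): √(1/75 + 1/99) = 0.1531.

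**4. The same check in the random-intercept model.** With ten complete time points, a patient mean has variance (1 + 9ρ)/10. At ρ = 0.5 this is 0.55, and the standard error is √(2 × 0.55/75) = 0.1211, whether 0, 24 or 2,400 controls without TENS are included. At ρ = 0.7 it is 0.1395, again unchanged by the 24. With simulated 25% dropout at ρ = 0.5 it is 0.12264 with or without the 24. The negligible remaining difference comes through the shared time slope.

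**5. Power for 75 versus 75.** 75 × 0.75 = 56.25, taken as 56 evaluable per arm.

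| Basis | 80% detectable difference | Power at 0.6 / 0.5 / 0.4 SD |
|---|---|---|
| One-time-point t-test, 56 per arm | 0.53 SD | 88% / 75% / 55% |
| One-time-point t-test, 75 per arm (withdrawals replaced) | 0.46 SD | 95% / 86% / 68% |
| Constant shift over ten time points, 56 per arm, ρ 0.5 to 0.7 | 0.39 to 0.45 SD | not tabulated |

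For the last row: 2.80 × √(2 × 0.55/56) = 0.39 and 2.80 × √(2 × 0.73/56) = 0.45. Treating the effect as a constant shift follows the section 9.4.4 equation. It is a simplification, because it includes the baseline measurement.

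**6. Margin.** On the first row, 0.60 − 0.53 = 0.07 SD, or 0.7 T-score points, separates the target from the 80% detectable difference.

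**The case against.** The strongest reply is that the conclusion survives even if the reason does not. The section 9.2 inputs need about 60 enrolled per arm and the plan has 75, so power at 0.6 SD exceeds 80% without the 24. That stands. A reader might infer that the trial is underpowered, but the documents do not show it.

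A reader might also infer that the 24 controls are useless throughout. They are not: they add precision to the retained by-arm ITT analysis, and in the TENS-term model they inform the TENS coefficient, the time slope and the variance components. The TENS-term model is described as additional. But the sentence at issue defends that model, and section 9.4.4 introduces it because it sees a risk of misidentifying the treatment effect by arm alone.

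It is also tempting to say that TENS in the control arm shrinks the effect, and to put a figure on the lost power. Section 4.2 says only that it may limit the effect and gives no amount. The values of 0.5 and 0.4 SD above are illustrations.

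The one-time-point figures ignore repeated measures, and section 7.2 says that withdrawn participants who received the intervention will be replaced. Both points stand, and both improve the detectable difference. No single figure should therefore be presented as the trial's power.

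Finally, section 9.4.4 does not say who the 20 are. Controls without TENS are the natural reading. Had they been 20 further patients split between the two TENS-era arms, they would help: at ρ = 0.5 the standard error would fall from 0.1211 to 0.1138. The request is therefore to reconcile the counts.

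**Conclusion.** The justification in section 9.4.4 is wrong as written. In the TENS-term model, study_arm has the precision of 75 kit versus 75 TENS controls, and the per-protocol analysis rests on the same two groups. The controls without TENS cannot pay for the extra term. The plan also leaves 20 unreconciled with 24, and does not say whether 0.6 SD remains apt for kit versus TENS.

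The consequence is limited. At 0.6 SD, power is about 88% under the least favourable basis tabulated (one time point, 56 per arm). On that basis it falls below 80% only if the true difference is under about 0.53 SD. If withdrawals are replaced, or the repeated measures are used with a correlation of 0.5 to 0.7, the threshold lies between about 0.39 and 0.46 SD. These figures assume two-sided testing and the stated 75 per arm. What is shown is an unsound justification, not a loss of power. The calculation it leans on is also misstated, at about twice the per-arm number its inputs give.

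**What to change.** 1. Delete the closing sentence of section 9.4.4.
2. Reconcile its count of 20 with the 24 in the synopsis and sections 4.1 and 6.2, and say who these subjects are.
3. State that study_arm in the TENS-term and per-protocol analyses rests on 75 kit versus 75 TENS controls, and that the 24 earlier controls add precision only to the by-arm ITT analysis.
4. Restate power and the 80% detectable difference for that contrast. Show the assumptions: test or model, sidedness, evaluable number, treatment of withdrawals, and any within-patient correlation. The table above can serve as the starting range. Say why 0.6 SD is still the target given section 4.2, or give power at smaller differences beside it.
5. In the same edit, correct 120 per arm and 245 in total in section 9.2. The stated inputs give about 60 per arm, about 120 in total.

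The cost is text only, with no extra patients. The downside is that the plan loses a convenient justification and must show less favourable power for effects below 0.6 SD.
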